7. ADVERSE EVENTS

7.1 Adverse Event Characteristics

• CTCAE term (AE description) and grade: The descriptions and grading scales found in the revised NCI Common Terminology Criteria for Adverse Events (CTCAE) version 4.0 will be utilized for AE reporting. All appropriate treatment areas should have access to a copy of the CTCAE version 4.0. A copy of the CTCAE version 4.0 can be downloaded from the CTEP web site http://ctep.cancer.gov/protocolDevelopment/electronic applications/ctc.htm.

• For expedited reporting purposes only:

- AEs for the agent(s) that are listed above should be reported only if the adverse event varies in nature, intensity or frequency from the expected toxicity information which is provided.

• **Attribution** of the AE:

- Definite The AE *is clearly related* to the study treatment.
- Probable The AE *is likely related* to the study treatment.
- Possible The AE *may be related* to the study treatment.
- Unlikely The AE *is doubtfully related* to the study treatment.
- Unrelated The AE *is clearly NOT related* to the study treatment.

7.2 Expedited Adverse Event Reporting

7.2.1 Investigators **must** report to the Overall PI any serious adverse event (SAE) that occurs after the initial dose of study treatment, during treatment, or within 30 days of the last dose of treatment on the local institutional SAE form.

7.2.2 DF/HCC Expedited Reporting Guidelines

Investigative sites within DF/HCC will report AEs directly to the DFCI Office for Human Research Studies (OHRS) per the DFCI IRB reporting policy.

7.3 Expedited Reporting to the Food and Drug Administration (FDA)

The Overall PI, as study sponsor, will be responsible for all communications with the FDA. The Overall PI will report to the FDA, regardless of the site of occurrence, any serious adverse event that meets the FDA's criteria for expedited reporting following the reporting requirements and timelines set by the FDA.

7.4 Expedited Reporting to AstraZeneca

A serious adverse event is any adverse event occurring at any dose or during any use of AZD1775 that:

- Results in death:
- Is life-threatening;
- Results in persistent or significant disability/incapacity;
- Results in or prolongs an existing inpatient hospitalization;
- Is a congenital anomaly/birth defect;
- Is a new cancer (that is not a condition of the study);
- Is associated with an overdose;
- Is an other important medical event

Serious adverse events that are ultimately related to disease progression do not need to be reported.

SAE information will be sent via secure e-mail connection or via fax within 24 hours of learning of the event. Medwatch 3500A report form with supporting relevant source documents (e.g. history and physical [H&P], hospital discharge summary, autopsy report when available, and results of relevant diagnostic tests completed to evaluate the event) will be attached and sent via:

- Secure email: [contact] by
- [contact]

Transmission of the SAE Report Form should be confirmed by the site personnel submitting the report.

Follow-up information for SAEs and information on non-serious AEs that become serious should also be reported to AstraZeneca as soon as it is available; these reports should be submitted using the MedWatch 3500A Form. The detailed SAE reporting process will be provided to the sites in the SAE reporting guidelines contained in the trial reference manual.

Investigators must report SAEs and follow-up information to their responsible Institutional Review Board (IRB) according to the policies of the responsible IRB. For fatal or life-threatening AEs where important or relevant information is missing, active follow-up is undertaken immediately.

7.5 Routine Adverse Event Reporting

All Grade 2 or higher Adverse Events must be reported in routine study data submissions to the Overall PI on the toxicity case report forms. AEs reported through expedited processes (e.g., reported to the IRB, FDA, etc.) must also be reported in routine study data submissions.

8. PHARMACEUTICAL INFORMATION

A list of the adverse events and potential risks associated with the investigational agents administered in this study can be found in Section 7.1.

8.1 AZD1775

8.1.1 **Description**

Systematic chemical name (IUPAC) is 2-Allyl-1-[6-(1-hydroxy-1-methyl-ethyl)-2-pyridyl]-6-[4-(4-methylpiperazin-1-yl)anilino]pyrazolo[3,4-d]pyrimidin-3-one hemihydrate. Other names include: MK-1775 hemihydrate, AZD1775 hemihydrate, and AZ13737568 hemihydrate. The molecular formula is C₂₇H₃₂N₈O₂ · 0.5H₂O and the relative molecular mass is 500.60.

8.1.2 Form

AZD1775 will be provided by AstraZeneca as summarized in Table 8-1.

Product Descriptions

Table 8-1

Product Name & Potency	Dosage Form
AZD1775 25mg	Capsule
AZD1775 100mg	Capsule

Supplies will be packaged in HDPE bottles.

8.1.3 Storage and Stability

Investigational clinical supplies must be received by a designated person at the study site, handled and stored safely and properly, and kept in a secured location to which only the investigator and designated assistants have access.

Storage condition: do not store above 30°C.

The clinical supplies storage area at the site must be monitored by the site staff for temperature consistency with the acceptable storage temperature range specified in this protocol or in the product label attached to the protocol. Documentation of temperature monitoring should be maintained.

8.1.4 Handling

Qualified personnel, familiar with procedures that minimize undue exposure to themselves and the environment, should undertake the preparation, handling, and safe disposal of the agent in a self-contained and protective environment.

In accordance with Good Pharmacy Practices, gloves should always be worn by study personnel if directly handling capsules that are returned (i.e. when counting returns). The Clinical Monitor should be contacted with any questions concerning investigational products where special or protective handling is indicated.

8.1.5 Availability

AZD1775 will be provided by AstraZeneca.

8.1.6 Ordering

Investigative sites will order their own agent. It is necessary to ensure that the pharmacy will be able to receive and store the agent. The IRB should be kept informed of who will supply the agent so that any regulatory responsibilities can be met in a timely fashion.

8.1.7 Accountability

The investigator, or a responsible party designated by the investigator, should maintain a careful record of the inventory and disposition of the agent using the NCI Drug Accountability Record Form (DARF) or another comparable drug accountability form. (See the NCI Investigator's Handbook for Procedures for Drug Accountability and Storage.)

8.1.8 **Destruction and Return**

Unused materials will not be returned and should be destroyed according to institutional policy.

8.2 Cisplatin

8.2.1 **Description**

The chemical name is cis-diamminedichloroplatinum(II). The Chemical structure is (SP-

4-2)-diamminedichloroplatinum platinum, diaminedichloro-, cis- (8CI). Cisplatin is also known as Platinol, CDDP. The molecular formula is Cl₂H₆N₂Pt. The molecular weight is 300.05.

Following cisplatin doses of 20 to 120 mg/m², the concentrations of platinum are highest in liver, prostate, and kidney; somewhat lower in bladder, muscle, testicle, pancreas, and spleen; and lowest in bowel, adrenal, heart, lung, cerebrum, and cerebellum. Platinum is present in tissues for as long as 180 days after the last administration.

Cisplatin does not undergo instantaneous and reversible binding to plasma protein that is characteristic of normal drug-protein binding. However, the platinum itself is capable of binding to plasma proteins, including albumin, transferrin, and gamma globulin. Three hours after a bolus injection and two hours after the end of a three-hour infusion, 90% of the plasma platinum is protein bound.

The parent compound, cisplatin, is excreted in the urine. Although small amounts of platinum are present in the bile and large intestine after administration of cisplatin, the fecal excretion of platinum appears to be insignificant.

Cisplatin decays monoexponentially with a half life of 20 to 30 minutes following administrations of 50 or 100 mg/m². Cisplatin has a plasma half-life of 30 minutes. The complexes between albumin and the platinum from cisplatin do not dissociate to a significant extent and are slowly eliminated with a minimum half-life of five days or more.

The renal clearance of free (ultrafilterable) platinum also exceeds the glomerular filtration rate indicating that cisplatin or other platinum-containing molecules are actively secreted by the kidneys. The renal clearance of free platinum is nonlinear and variable and is dependent on dose, urine flow rate, and individual variability in the extent of active secretion and possible tubular reabsorption.

8.2.2 Form

Commercially available cisplatin injection infusion (1mg/ml): Each ml of sterile, unpreserved solution contains: 1.0mg of cisplatin with 9 mg of sodium chloride and 1mg of mannitol in water for injection. Hydrochloric acid is added to adjust the pH. Singledose glass vials of 10, 50, and 100mL contain 10, 50, and 100mg of cisplatin respectively.

8.2.3 Storage and Stability

Vials of cisplatin injection, USP, are stored at room temperature between 15°C and 25°C. Do not refrigerate or freeze cisplatin solutions, since a precipitate will form. IV needles, syringes, or sets having aluminum components should not be used in preparing or administering cisplatin solutions. An interaction will occur between aluminum and

platinum from cisplatin, causing a black precipitate that is visible in cisplatin solution.

8.2.4 Handling

Qualified personnel, familiar with procedures that minimize undue exposure to themselves and the environment, should undertake the preparation, handling, and safe disposal of the chemotherapeutic agent in a self-contained and protective environment.

8.2.5 Availability

Cisplatin is commercially available.

8.2.6 Preparation

Cisplatin should be prepared according to institutional guidelines.

8.2.7 Ordering

Cisplatin is commercially available. Check with the site Director of Pharmacy and/or the site research pharmacy to ensure that the agent is in stock. If the agent is not stocked, ensure that the agent can be ordered **before** the protocol is activated.

9. BIOMARKER, CORRELATIVE, AND SPECIAL STUDIES

9.1 Biomarker Studies

All biomarker analyses completed on blood and tissue samples for correlative data will be exploratory.

Weel kinase is a regulator of the G2/M checkpoint. As Weel phosphorylates CDC2 in response to genotoxic insults, inhibition of CDC2 phosphorylation by a Weel inhibitor is considered a direct measure of target engagement. Under normal conditions, pCDC2 levels in tissue is quite low. Changes in pCDC2 is contingent upon pCDC2 induction by DNA damage. Patients will therefore undergo tumor biopsies after one dose of cisplatin, and then again after a dose of cisplatin + AZD1775.

Formalin-fixed, paraffin-embedded (FFPE) biopsy specimens will be subjected to immunohistochemical analyses using standard procedures for: (1) Total CDC2; (2) phospho-CDC2; (3) gamma-H2AX; (4) phospho-Histone 3; and (5) cleaved caspase 3.

For total CDC2, phospho-CDC2, phospho-Histone 3 and cleaved caspase 3, immunohistochemical sections will be scored manually and the % positive cells will be annotated; a minimum of 200 cells will be counted. Additionally, stained slides will be scanned using an Aperio ScanScope XT workstation (Aperio Technology, Inc., Vista, CA). Images will be visualized and digitally annotated (as regions of interest, ROIs) using ImageScope software (version 10.0.35.1800, Aperio Technology). The ROIs will then be analyzed using a standard

analysis algorithm to quantitate the proportion of area that is positive for staining (color deconvolution v9.0, Aperio Technology). The expected result after cisplatin/AZD1775 compared to cisplatin alone is preserved total CDC2 staining, reduced phospho-CDC2 staining, increased phospho-Histone 3 staining and increased cleaved caspase 3 staining. In phase 1 studies, in which skin biopsies were analyzed, a decrease of phospho-CDC2 in the presence of AZD1775 of at least 50% was considered to represent evidence of target engagement. In a study of AZD1775 monotherapy, increases in gamma-H2AX were seen in 3 of 5 paired biopsies. We will analyze changes in phospho-CDC2 (using this parameter alone); additionally, the change in ratio of phospho-CDC/total CDC2 will also be assessed when biopsies post-cisplatin/AZD1775 and post-cisplatin alone are compared.

Immunohistochemistry for gamma-H2AX [pSer139] will be scored manually with a determination of the percentage of cells containing at least 5 nuclear foci.^{3,4} It is expected that the percentage of foci-positive cells will be greater after cisplatin/AZD1775 compared to cisplatin alone. This work will be performed in collaboration with [name], who was the DF/HCC PI on the Phase I trial of chemotherapy combinations with AZD1775, and [name] [name], who is internationally recognized expertise in the assessment of DNA damage pathways, and with [name], a pathologist in the DF/HCC Pathology Core at Brigham and Women's Hospital, who has extensive experience with analysis of these markers.

The study will obtain paired tumor biopsies for all patients enrolled with accessible disease (after cisplatin monotherapy and after cisplatin + AZD1775 combination therapy). The analysis will treat the quantification of pCDC2, gamma-H2AX, phospho-Histone 3, and cleaved caspase 3 as continuous variables. To evaluate change in these marker levels after the addition of AZD1775, descriptive statistics for the change will be generated. Paired t-tests or Wilcoxon signed rank test, whichever is appropriate considering the data distribution, will also be used to describe change in marker levels.

Biopsy samples will also be subjected to whole exome sequencing (WES) to capture (1) BRCA reversion mutations as well as the mutation status of most genes involved with double strand break repair (2) evidence of telometric allelic imbalance, a predictor of cytotoxic therapy response⁵, (3) overall mutational signature, and (4) cell cycle genes related to G1/S checkpoint, that may enhance reliance on Wee1-mediated G2/M checkpoint for proper DNA repair.⁶

The prevalence of BRCA 1 and BRCA2 mutations is approximately 10-15% among patients with triple-negative breast cancer.³⁷ Breast cancers with BRCA deficiency may be more susceptible to increases in DNA damage provoked by combination therapy with cisplatin and AZD1775. For patients in whom BRCA status is unknown, anonymized blood samples will be undergo testing for BRCA 1 and 2. We will determine whether there is an association between germline BRCA deficiency and response to therapy.

To evaluate the relationship between BRCA status and response, the data will be tabulated and Fisher's exact test will be applied, recognizing that only large differences are detectable if the overall response rate is 30% (78% power to detect response rate of 83% among BRCA+ and 20% among BRCA- assuming 15% of patients are deemed BRCA+ and data are available for all 35 patients).

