1.3 Secondary Objectives

The secondary objectives of the study are:

- 1) To evaluate Progression Free Survival (PFS).
- 2) To evaluate change in pCDC2 after therapy with AZD1775 in paired biopsies
- 3) Evaluate incidence of p53 mutations in tumor tissue and correlate mutational status with response
- 4) To evaluate change in markers for DNA damage (gamma-H2AX, phospho-Histone 3, and caspase 3) after exposure to cisplatin + AZD1775 compared to cisplatin therapy alone in paired biopsy samples
- 5) To evaluate the incidence BRCA1 and BRCA2 mutations, and correlate mutational status with response

- 6) To explore other possible gene mutations that may correlate with response.
- 7) To correlate next generation sequencing of tumors with participant outcomes (ORR and PFS) in DFCI participants only.

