2.5 Correlative Studies Background

We plan to demonstrate target engagement in tumor tissue by analysis of changes in pCDC2. Changes in pCDC2 have been seen in skin biopsies of patients receiving AZD1775, ²⁶ and recently has also been demonstrated in 3 of 5 paired biopsies in patients receiving AZD1775 as monotherapy in a phase 1 trial (REF: Do et al., JCO 2015).

Patients will receive cisplatin monotherapy for 1 cycle upfront, followed by cisplatin + AZD1775 for subsequent cycles of therapy. Any patient with tumor that is accessible to biopsy will undergo research biopsies after one dose of cisplatin, and after the combination therapy. We anticipate that pCDC2 will be present after cisplatin monotherapy. After the combination, a reduction in pCDC2 relative to CDC2 is expected. This should be accompanied by evidence of checkpoint bypass and entrance of tumor cells into mitosis, which will be assessed by an increase in phospho-Histone 3 after combination treatment compared to cisplatin monotherapy. Checkpoint bypass will result in greater DNA damage, which should cause an increase in gamma-H2AX after combination treatment.²⁷ Finally, entrance of cells into mitosis without adequate DNA repair is frequently lethal and should result in increased apoptosis, which can be assessed with an increase in cleaved caspase 3 after combination treatment.²⁸

Historically, it has been challenging to study the molecular evolution of tumors over time and through progression on serial treatment regimens. However, emerging technology now permits whole exome sequencing from cell-free DNA (cfDNA) isolated from fresh blood. We aim to examine the utility of this approach for detecting molecular changes in individual patients' tumor cell populations over time by performing serial cfDNA.

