Ototoxicity has been observed in up to 31% of subjects treated with a single dose of cisplatin (50mg/m²) and is manifested by tinnitus and/or hearing loss in the high frequency range (4000 to 8000 Hz). Decreased ability to hear normal conversational tones may occur occasionally. Ototoxicity can be more severe in children than in adults and more frequent and severe with repeated administration. Hearing loss can be unilateral or bilateral and is usually not reversible. During treatment with cisplatin, it is necessary to monitor hearing at each visit as part of a standard physical exam.

Myelosuppression

Myelosuppression occurs in 25 to 30% of subjects treated with cisplatin. The nadirs in circulating platelets and leukocytes occur between days 18 and 23, with most subjects recovering by day 39. Leukopenia and thrombocytopenia are more pronounced at higher doses (>50 mg/m²). Anemia (a decrease in hemoglobin of 2 gm/100ml) occurs at approximately the same frequency and with the same timing as leukopenia and thrombocytopenia.

Neurotoxicity

Cisplatin neurotoxicity is characterized by peripheral neuropathies, which are sensory in nature but can also include motor difficulties such as reduced deep-tendon reflexes and leg weakness. The symptoms usually occur after prolonged therapy (4 to 7 months). Cisplatin therapy should be discontinued when serious neuropathy develops. The neuropathy, however, may progress

further even after discontinuation of treatment.

Hematologic Toxicity

Dose adjustment at the start of a subsequent cycle of therapy will be based on the neutrophil and platelet counts on day 1 of the cycle. ANC must be $\geq 1.0 \times 10^9 / L$ and platelets $\geq 75 \times 10^9 / L$ before the start of each cycle. Treatment should be delayed to allow sufficient time for recovery. Upon recovery, if treatment is resumed, it should be accounting to the guidelines in Table 6-2 with respect to nadir platelet and ANC values for subsequent cycles, except as noted below. A delay in treatment due to hematologic toxicity if more than 3 weeks will result in withdrawal from the study.

The use of colony stimulating factors (filgrastim or pegfilgrastim) is permissible if recommended by the primary treating physician but should be clearly recorded in the medical record and case report form. Prophylactic use of GCSF is not recommended with the first cycle.

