If GCSF is initiated, then the required dose modification will be adjusted according to the guidelines in footnote of Table 6-3.

Table 6-3
Dose Adjustments for Cisplatin Based on Hematologic Values for Preceding Cycle

Platelets (×1	0 ⁹ /L)	ANC (×10 ⁹ /L)	Dose of Cisplatin
≥75	and	≥1.0	75mg/m ^{2*}
≥50	or	≥ 0.5	60mg/m ^{2*} ,#
< 50	or	<0.5	50mg/m^{2*} ,@
Recurrence of	grade 3 or 4 th	rombocytopenia after 2 dose reductions	Withdraw subject from study
or			continue on ADZ1775
alone			
Recurrence of	grade 3 or 4 ne	utropenia after 2 dose reductions	Withdraw subject from study
or			
			continue on ADZ1775
alone			

^{*} Treatment should be delayed until recovery of platelets to $\geq 100 \times 10^9 / L$ and ANC to $\geq 1.0 \times 10^9 / L$.

Non-Hematologic Toxicity

For other grade 3 or higher non-hematologic effects (with the exception of grade 3 transaminase elevations and nausea or vomiting), treatment should be delayed until resolution (less than or equal to baseline). Treatment can be resumed at 60mg/m², if deemed appropriate by the treating physician, for all subsequent cycles.

Neurosensory Toxicity

[#] For ANC ≥0.5 treat at 75mg/m² dose if initiating GCSF

[@] For ANC<0.5 treat at 60mg/m² dose if initiating GCSF

Adjustments of the cisplatin dose in subjects with neurosensory toxicity are shown in Table 6-4. Cisplatin therapy should be held for grade 2 or higher neurosensory toxicity and should resume with a dose reduction once it has resolved to grade 1.

Table 6-4
Dose Adjustments for Cisplatin Based on Neurosensory Toxicity

CTCAE Grade	Dose of Cisplatin
0-1	100% of previous dose
2	60mg/m^2
3-4	Withdraw participant from study or continue on AZD1775
alone	

Tinnitus or Significant Hearing Loss

In cases of tinnitus or significant hearing loss, cisplatin therapy should be reduced or stopped, at the discretion of the investigator.

Nephrotoxicity

Cisplatin dose adjustments in subjects with renal toxicity are shown in Table 6-5. Either serum creatinine or estimated creatinine clearance may be used. If a dose delay or dose reduction occurs due to nephrotoxicity, subsequent doses of cisplatin may be escalated based on the renal function on the day of treatment (+/- 3 days) and should be determined based on Table 6-5.

Table 6-5
Cisplatin Dose Adjustments for Renal Toxicity

Creatinine(mg/dl)	OR Creatine Clearance(cc/min)	Dose of Cisplatin
<1.6	>50	75mg/m^2
1.6-2	10-50	60mg/m^2
>2	<10	Delay one week

Other Toxicity

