13.3 Analysis of Secondary Endpoints

PFS is defined as the time from enrollment until disease progression or death, whichever occurs first. Patients alive and free from disease progression will be considered censored. PFS will be estimated by the method of Kaplan and Meier.

The study requires paired biopsies from all patients with accessible tumor. With a sample size of 37 and assuming that 50% of them either without accessible lesions or assay failure, paired biopsy assessment are available for 18 patients. Assuming the percent of pCDC2 positive cells decreases 50% in the presence of AZD1775 and the standard deviation of pCDC2 equals to the difference, using t statistics with 1-sided alpha of 0.05, there will be 99% power to detect the change in pCDC2 pre- and post-treatment. The calculation was done using East v6.3 (Cytel Inc). Analysis plan for all biomarker data was written in section 9.1.

Difference of % CDC2	S.d. of paired difference	Power
positive cells in paired		
samples		
0.5	0.5	99%
0.5	0.75	86%
0.5	1	65%

Descriptive statistics will be used to characterize the tumor genomic profiles available for DFCI participants by disease response to therapy (response assessed by RECIST 1.1). PFS and ORR will be estimated using Kaplan-Meier methods among patients with and without certain gene mutations, respectively. The Benjamini-Hochberg procedure will be used to control the false discovery rate and address multiple comparisons.

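### The paired-biopsy analysis reads the whole marker change as the AZD1775 effect, although cycle 2 cisplatin may be lower than cycle 1; an equal-dose sensitivity analysis and a listing of doses are missing.

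*Combined protocol and SAP*

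**What the plan says.** Section 1.3 sets two paired-biopsy objectives: the change in pCDC2 (objective 2), and the change in gamma-H2AX, phospho-Histone 3 and caspase 3 "after exposure to cisplatin + AZD1775 compared to cisplatin therapy alone in paired biopsy samples" (objective 4). Section 2.5 gives the purpose: "We plan to demonstrate target engagement in tumor tissue by analysis of changes in pCDC2".

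The analysis is in Section 9.1: "To evaluate change in these marker levels after the addition of AZD1775, descriptive statistics for the change will be generated". It continues: "Paired t-tests or Wilcoxon signed rank test, whichever is appropriate considering the data distribution, will also be used to describe change in marker levels". All pairs enter. Cisplatin dose plays no part as a restriction, an adjustment or a listed item. The same section explains why the first biopsy follows cisplatin: "Changes in pCDC2 is contingent upon pCDC2 induction by DNA damage". It also calls all biomarker analyses exploratory.

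Section 6.2 starts cisplatin at 75 mg/m2 and allows 60 or 50 mg/m2 in later cycles. Table 6-3 is titled "Dose Adjustments for Cisplatin Based on Hematologic Values for Preceding Cycle", and Tables 6-4 to 6-6 add neurosensory, renal and other triggers. The biopsy rules (Sections 3.1.12 and 9.2.3.2, and Section 10 footnote i) deal with timing and delay, and do not mention a reduced cisplatin dose.

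**The concern.** In a single-arm trial, the cycle 1 biopsy is the only control for the cycle 2 biopsy. The within-patient difference isolates AZD1775 only if the background treatment is alike in both cycles. Where cycle 2 cisplatin is lower, two things change at once: AZD1775 is added and the DNA-damaging dose falls. On the protocol's own account pCDC2 appears in response to that damage, so both changes could push pCDC2 down.

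Gamma-H2AX and caspase 3 are expected to rise with the combination, so less cisplatin may hide an effect on them. For phospho-Histone 3 the direction is uncertain. Section 2.5 uses it as a marker of entry into mitosis, and less damage could mean less arrest and a higher value.

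At stake is the target-engagement statement, which could mix a drug effect with a background-dose effect without the reader being able to tell.

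**Working it through.** **1. Can the doses differ at cycle 2?** Yes. Section 6.2 bases the haematologic adjustment on day 1 counts of a subsequent cycle, and cycle 2 is the first such cycle. The nadir it gives (days 18 to 23) spans cycle 2 day 1, which is day 22. The advice in Section 6.1 to modify AZD1775 first does not prevent this, because AZD1775 is not given in cycle 1. Tables 6-5 and 6-6 also disagree on the dose for the same creatinine band (60 against 50 mg/m2) and must be reconciled.

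**2. Does the pCDC2/total CDC2 ratio in Section 9.1 remove the problem?** No. It corrects for the amount of CDC2 protein, not for weaker induction of the phosphorylated form.

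**3. Reproduce the plan's power.** Section 13.3 says "there will be 99% power to detect the change in pCDC2 pre- and post-treatment". Its inputs are n = 18 pairs, difference 0.5, and one-sided alpha 0.05.

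Formula: power = P(T > t(0.95; 17)), where T is noncentral t with 17 df and noncentrality (difference/SD) × √18. The critical value is 1.740.

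| SD | Noncentrality | Power | Stated |
|---|---|---|---|
| 0.5 | 4.243 | 0.992 | 99% |
| 0.75 | 2.828 | 0.857 | 86% |
| 1 | 2.121 | 0.652 | 65% |

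The plan's figures are right. They treat the whole 0.5 as the AZD1775 effect.

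**4. Illustrate the effect of unequal doses.** These assumptions are not in the documents: cycle 1 pCDC2 level set to 1, induction proportional to cisplatin dose, no AZD1775 effect, and SD unchanged by the mixture. The share f of pairs reduced is not stated, so I use 10%, 20% and 30%. Section 6.2 says "Myelosuppression occurs in 25 to 30% of subjects treated with cisplatin", which gives only a scale: it is not a cycle 2 dose-reduction rate.

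Fall in a reduced pair: 1 − 60/75 = 0.20, or 1 − 50/75 = 0.333. Mean fall over all pairs = f × that fall. The rejection rate uses the formula in step 3 with this mean as the difference.

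| f | Reduced to (mg/m2) | Mean fall | SD 0.5 | SD 0.75 | SD 1 |
|---|---|---|---|---|---|
| 10% | 60 | 0.020 | 0.069 | 0.062 | 0.059 |
| 10% | 50 | 0.033 | 0.085 | 0.072 | 0.066 |
| 20% | 60 | 0.040 | 0.094 | 0.077 | 0.069 |
| 20% | 50 | 0.067 | 0.135 | 0.100 | 0.085 |
| 30% | 60 | 0.060 | 0.124 | 0.094 | 0.081 |
| 30% | 50 | 0.100 | 0.203 | 0.135 | 0.108 |

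The nominal rate is 0.05. The mean fall from dose alone is 4% to 20% of the planned 0.5 (0.02/0.5 to 0.10/0.5).

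**5. Compare with the engagement threshold.** Section 9.1 cites a fall of at least 50% as evidence of engagement in earlier skin-biopsy work. Under these assumptions a reduced pair falls by 20% or 33%, so dose alone does not reach it.

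**The case against.** The strongest case against runs as follows.

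- **Status.** Section 9.1 calls these analyses exploratory and uses the tests to describe change. This stands, and it limits the weight of the point. Even so, Section 13.3 gives pCDC2 a formal one-sided power calculation, and a descriptive summary is equally confounded if doses are not shown.
- **No dose-response is given.** The protocol says the pCDC2 change depends on damage, not that 60 mg/m2 induces less than 75 mg/m2. Section 8.2.1 adds that platinum persists in tissue for as long as 180 days, and the second biopsy follows a second dose. This stands. A reader might infer that the error always runs toward false engagement, but the documents do not support that.
- **The top figure stacks assumptions.** A rate of 0.20 needs 30% of pairs, all at 50 mg/m2, at the smallest SD. The footnotes to Table 6-3 give higher cisplatin doses for low neutrophil counts when GCSF is started. If the cycle 1 level were 0.5 instead of 1, the same scenario at SD 0.5 would give 0.108. This stands. Nor is the myelosuppression figure an upper bound on reductions: it states no grade or cycle, and renal and other toxicities also lower the dose.
- **Restriction has its own faults.** Equal-dose pairs are selected on tolerance of cycle 1. They also still differ in time since cisplatin: 5 to 48 hours at the first biopsy, and about 53 to 56 hours (± 24) at the second if both drugs start together (last dose at 4 × 12 = 48 hours, plus 5 to 8). Pairs may be few: Section 1.1 promises at least 10 biopsied patients, and Section 9.2.3.8 reports eight with paired tissue for another assay. This stands, and it argues against making the restricted set the main analysis.

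What survives all four is the gap itself: nothing in the plan lets a reader separate the two sources of change.

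**Conclusion.** The point holds as a gap in an exploratory secondary analysis. Section 9.1 attributes the cycle-to-cycle change to AZD1775, Section 6.2 lets the background cisplatin dose differ, and no section restricts, adjusts for or lists that dose. Only pairs with a cycle 2 reduction are affected, and their number is unknown.

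Under the stated assumptions, the one-sided false-positive rate for pCDC2 rises from 0.05 to 0.07-0.20 at SD 0.5, 0.06-0.14 at SD 0.75 and 0.06-0.11 at SD 1. These figures show scale and are not estimates. A reader might infer that reduced cisplatin could by itself produce the plan's target-engagement result. The documents do not support this: even with induction strictly proportional to dose, the fall in a reduced pair is 20% to 33%, below 50%. The risk is an inflated effect, or a smaller false one, for pCDC2; a possibly hidden effect for gamma-H2AX and caspase 3; and an unknown direction for phospho-Histone 3. The primary response-rate analysis is untouched.

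**What to change.** In Section 9.1, for objectives 2 and 4:

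1. Keep all pairs as the main analysis.
2. Prespecify a sensitivity analysis limited to pairs with the same cisplatin mg/m2 dose in both cycles (within the 5% rounding that Section 5.3.2 allows) and with AZD1775 taken before the second biopsy.
3. List the cisplatin dose of each cycle beside each pair.
4. Attribute the change to AZD1775 only if the equal-dose result agrees with the main result in direction and size.

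The cost is one paragraph of wording. The data are the dosing records and the medication diary already required. The downside is lower precision in the restricted set: going from 18 to 13 pairs takes power from 99% to 96% at SD 0.5, and from 86% to 73% at SD 0.75. The loss is larger if few pairs exist; going from 8 to 6, for example, takes power from 82% to 68% at SD 0.5. Agreement should therefore be judged on the estimates and their intervals, not on significance. The restricted set does not remove the difference in time since cisplatin, which should be stated with the result. No change to dosing is proposed.
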